8.3.3.2 Suspected Adverse Drug Reactions/Adverse Reactions

A Suspected Adverse Drug Reactions (ADR) includes any noxious and unintended reaction to an investigational medicinal product, regardless of dose administered. Unlike AEs, in the case of an adverse reaction a causal relationship between a medicinal product or study treatment and an AE is at least a reasonable possibility.

8.3.4 Assessment of Causality of Adverse Event

The Investigator is required to provide a causality assessment for each AE reported to the Sponsor. The Sponsor will consider the Investigator's causality assessment and also provide its own assessment.

Causal relationship to the study drug will be established according to medical judgment on whether there is a **reasonable possibility of a causal relationship between the AE and the IMP administration:**

The Investigator must determine and classify the AE causality according to the following categories:

- **Not related:** There is not a reasonable possibility of causal relationship between the AE and the study drug.
- **Related:** There is evidence to suggest a causal relationship between the study drug and the AE.

Criteria to assess the causal relationship should take into account of the following conditions: 1) a plausible temporal sequence from the study drug administration to the AE onset; 2) whether the event follows a known response pattern to the suspected treatment; 3) whether the AE could be reasonably explained by the subject's clinical state, comorbidities, or concomitant medications, as well as 4) the occurrence of improvement on stopping/reducing the treatment (positive dechallenge) and/or reappearance of the event on repeated exposure (positive rechallenge).

8.3.5 Severity of Adverse Event or Suspected Adverse Drug Reaction

AEs and suspected ADRs will be classified depending on their severity according to the following definitions:

Mild: an AE which is well tolerated by the subject, causing minimum degree of malaise and without affecting normal activities.

Moderate: an AE that interferes with the subject's normal activities.

Severe: an AE that prevents the subject from performing their normal activities.

AE and suspected ADR severity gradation must be distinguished from AE and suspected ADR seriousness gradation, which is defined according to event consequence. For example, headache can be mild, moderate or severe but not necessarily serious in all these cases.

The Investigator will be responsible for assessing the AE and suspected ADR intensity during the clinical trial, taking into account current criteria included in this section.

8.3.6 Expectedness of Adverse Event or Suspected Adverse Drug Reaction

An AE or suspected ADR is considered “unexpected” if the nature, seriousness, severity or outcome of the reaction(s) is not consistent with the reference information. The expectedness shall be determined by the Sponsor according to the reference document for any serious ADRs (potentially related SAEs) for expedited safety reporting purposes.

8.3.7 Seriousness of Adverse Event or Suspected Adverse Drug Reaction

An AE or suspected ADR is considered “serious” if, in the view of either the Investigator or Sponsor, it results in any of the following outcomes:

- Death
- Life-threatening AE (life-threatening in the definition of “serious” refers to an event in which the subject was at risk of death at the time of the event; it does not refer to an event which hypothetically might have caused death if it were more severe)
- In-patient hospitalization or prolongation of existing hospitalization
- A persistent or significant incapacity or substantial disruption of the ability to conduct normal life functions
- A congenital anomaly/birth defect
- An important medical event (important medical event in the definition of “serious” refers to those events which may not be immediately life-threatening, or result in death, or hospitalization, but from medical and scientific judgment may jeopardize the subject or/and may require medical or surgical intervention to prevent one of the other outcomes listed above).

*Hospitalization is to be considered only hospital stay for equal or more than 24 hours. The following hospitalizations should not be reported as SAEs:

- Hospitalization or prolongation of hospitalization needed for procedures required by the clinical trial protocol.

- Hospitalization or prolongation of hospitalization as part of a routine procedure followed by the center.
- Hospitalization for a survey visit, annual physicals, or social reasons.
- Elective or pre-planned hospitalizations for a pre-existing condition that had not worsened from Baseline (e.g. elective or scheduled surgery arranged prior to start of the study).
- Admissions not associated with an AE (e.g. social hospitalization for purposes of respite care).

This definition permits either the Sponsor or the Investigator to decide whether an event is “serious”. If either the Sponsor or the Investigator believes that the event is serious, the event must be considered “serious” and evaluated by the Sponsor for expedited reporting.

8.3.8 Adverse Event Documentation

For subjects receiving at least one dose of the IMP, all AEs and SAEs occurring after the subject has **signed the ICF through the Final Visit (i.e., end of study)** must be fully recorded in the subject's eCRF, and SAE form (if serious) as well as in the medical record. For subjects who do not receive at least one dose of the IMP (e.g. screening failure subjects), all SAEs occurring after the subject has **signed the ICF through the until subject withdrawal** must be fully recorded in the subject's eCRF, and SAE form as well as in the medical record. If no AE has occurred during the study period, this should also be indicated in the eCRF.

It is the responsibility of the Investigator to ensure that AEs are appropriately recorded.

At each visit, AEs will be elicited by asking the individual a non-leading question such as “Do you feel different in any way since the last visit?” Moreover, AEs will also be collected through directly observed events or spontaneously volunteered by the subject. Clearly related signs, symptoms and abnormal diagnostic procedures should preferably be grouped together and recorded as a single diagnosis or syndrome wherever possible.

The following variables must be recorded in the AE eCRF:

- The verbatim term (a diagnosis is preferred)
- Date/time of onset
- Date/time of resolution
- Severity (mild, moderate, severe)
- Causality (unrelated, possibly related, definitely related)*
- Seriousness (yes, no)
- Action taken (with regard to IMP)
- Other action (to treat the event)
- Outcome and sequel (follow-up on AE)

*Causality assessment will be made only when the AE occurs after the subject has received at least one dose of the IMP. An AE occurring before subject's exposure to IMP will be always labeled as "unrelated".

In addition to the Investigator's own description of the AEs, each AE will be encoded according to the Medical Dictionary for Regulatory Activities (MedDRA).

For example, a laboratory test abnormality considered clinically significant, eg, causing the subject to withdraw from the study, requiring treatment or causing apparent clinical manifestations, or judged clinically significant in the context of the subject's medical history by the Investigator, should be reported as an AE. Each event must be described in detail along with start and stop dates, severity, relationship to IMP, action taken and outcome. Each event must be adequately supported by documentation as it appears in the subject's medical or case file.

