7.2 Summary of Primary Safety Outcome

7.2.1 Adverse Events

Adverse events will be classified as Treatment-Emergent AEs (TEAEs) or non-Treatment-Emergent AEs (non-TEAEs), based on the comparison of the AE onset date/time with the start date/time of study treatment.

- A TEAE will be defined as an AE which starts or worsens in severity during or after the first administration of study treatment.
- A non-TEAE will be defined as an AE which starts or worsens in severity prior to the start of the first administration of study treatment.

The following algorithm will be used to identify the treatment group under which each AE will be summarized:

For SAESIs:

- AEs that start or worsen in severity at any time after a patient's first dose of ABvac40 will be associated with the ABvac40 treatment group.
- AEs that start or worsen in severity after first dose of Placebo, but before first dose of ABvac40, will be associated with the Placebo treatment group

For non-SAESIs:

- For patients randomised to the ABvac40 arm Part A / Placebo+Booster arm Part B treatment sequence:
 - AEs that start or worsen in severity at any time during or after a patient's first dose of study drug in part A and prior to their booster ABvac40 vaccination will be associated with the treatment received at their last injection prior to the AE.
 - AEs that start or worsen in severity during or after a patient's booster ABvac40 vaccination will be associated with the ABvac40 treatment group.
- For patients randomised to the Placebo arm Part A / ABvac40 arm Part B treatment sequence:
 - AEs will be associated with the treatment received at their last injection prior to the AE.

For the purposes of classifying AEs as treatment emergent and to assign treatment groups, partial AE start and end dates will be imputed to allow comparison with the study treatment date start and end dates. Section 9.1.1 below presents the imputation rules. Note, the imputed dates will be used for classification purposes and treatment group assignment purposes only and the original partial AE dates will be presented in data listings.

An overall summary of AEs will be presented by treatment group, by providing counts and percentages of patients with any: TEAE, non-TEAE, Treatment related TEAEs, TEAE leading to treatment discontinuation, TEAEs leading to death, Treatment-Emergent Serious AE (TESAE), Treatment-

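### For patients given placebo first, the SAP's rule for assigning ordinary AEs omits worsening and the listed AE fields carry no date for it, so worsening after ABvac40 can be counted under Placebo

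*Protocol*

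**What the plan says.** **What is collected.** Protocol section 8.3.8 introduces its AE fields with "The following variables must be recorded in the AE eCRF". The list includes "Date/time of onset", the matching time of resolution and one three-grade severity item. Section 8.3.3.1 likewise lists start date, end date and intensity. Neither section lists a date of severity change, says whether severity means the grade at onset or the worst grade, or gives a general instruction to open a new entry when an ongoing AE gets worse.

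Some kinds of worsening do have rules:
- Worsened examination, EKG and MRI findings are recorded as AEs (8.2.4 to 8.2.6).
- Deterioration of Alzheimer signs or laboratory values present at the first assessment can count as an AE (8.3.3.1).
- New micro-haemorrhages after an intervening dose are a new ARIA-H with a new SAE form (8.3.10.1).

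**How it is classified.** SAP section 7.2.1 states: "A TEAE will be defined as an AE which starts or worsens in severity during or after the first administration of study treatment". The same section says the classification is "based on the comparison of the AE onset date/time with the start date/time of study treatment", and Appendix 9.1.1 deals only with AE start and end dates. Treatment group is then assigned as follows:
- SAESIs, both sequences: "AEs that start or worsen in severity at any time after a patient's first dose of ABvac40 will be associated with the ABvac40 treatment group".
- Non-SAESIs, ABvac40-first sequence, from the Part B booster on: "AEs that start or worsen in severity during or after a patient's booster ABvac40 vaccination will be associated with the ABvac40 treatment group". Before the booster, events that start or worsen go with the last injection.
- Non-SAESIs, placebo-first sequence: "AEs will be associated with the treatment received at their last injection prior to the AE".

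**The concern.** AEs are the primary safety variable. SAP section 3 presents them by ABvac40 and Placebo across both parts, and section 7.2.1 adds tables by maximum severity. Every patient who enters Part B is planned to receive both products, so the attribution rule decides in which column a Part B event appears.

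The placebo-first patients receive their first ABvac40 doses in Part B. Theirs is the one sequence whose rule leaves worsening out. An ordinary event that begins on placebo and gets worse after vaccination could then stay in the Placebo column, and the ABvac40 column would understate the severity reached under vaccine. A second gap lies underneath: where the SAP does use worsening, no listed field says when it happened.

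**Working it through.** The plan states no figure on this point, so the check is to run one case through the rules. The case is a mild AE with onset after a placebo injection that becomes severe after ABvac40. The documents do not fix how it would be recorded, so four conventions are tried:
- A: one record, onset kept, severity overwritten to the worst grade.
- B: one record, severity left as at onset.
- C: a new record at worsening, with its own onset.
- D: one record at worst severity, plus a date of worsening.

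| Convention | Placebo first, non-SAESI | Placebo first, SAESI | ABvac40 first, non-SAESI (onset after a Part B placebo injection, severe after the V13B booster) |
|---|---|---|---|
| A | severe, Placebo | severe, Placebo | severe, Placebo |
| B | mild, Placebo | mild, Placebo | mild, Placebo |
| C | mild, Placebo; severe, ABvac40 | mild, Placebo; severe, ABvac40 | mild, Placebo; severe, ABvac40 |
| D | severe, Placebo | severe, ABvac40 | severe, ABvac40 |

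SAESIs in the ABvac40-first sequence always go to ABvac40 in this case, because the first ABvac40 dose was given in Part A.

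Three things follow.

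1. With only the listed fields (A or B), the worsening is not credited to ABvac40 in any of the three columns. Under A its severity is shown under Placebo; under B it is not shown.
2. A date of worsening alone (D) repairs the second and third columns but not the first. There the rule looks only at the last injection before the AE, so the wording must change as well.
3. A new record at each worsening (C) gives the intended attribution in every column, even under the present rule. No general instruction in the protocol or SAP requires it.

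**Treatment-emergent status.** Take an AE that starts before the first dose and worsens after it. It is treatment-emergent by definition, but a comparison of onset with treatment start cannot show that. The non-treatment-emergent definition also covers events that start or worsen before the first dose, so this AE meets both definitions.

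**Size.** A count would need the number of placebo patients entering Part B, the share with an AE ongoing at V1B, and the share of those that worsen after ABvac40. The documents give none of these. The 35 per group in Protocol section 9.2 is expected per-protocol completion, not Part B entry.

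**The case against.** The strongest reply is that section 8.3.8 is a list of required variables, not the form. Data-entry rules sit in a Data Entry Manual (Protocol section 11.3.2) that is not among the documents, and it may already require a new record on worsening. The SAP's tables expect several AEs with the same preferred term in one patient, which fits that practice. This stands as a limit on the conclusion: the error can occur, but is not shown to occur. It does not answer the SAP wording, which omits worsening in one sequence and would leave the event under Placebo even if a date of worsening were collected.

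It is also fair that much worsening is covered by the examination, EKG, MRI, laboratory, Alzheimer-sign and ARIA-H rules. Worsening that makes an event serious also brings an SAE report and an individual listing. What remains is mainly reported symptoms.

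Four stronger readings are tempting and are not supported:
- **That such an event will appear as a severe Placebo event.** With a single record on the listed fields, that needs the grade to be overwritten to the worst; the documents do not say so.
- **That the gap always favours ABvac40.** With a single record, an AE that starts on ABvac40 in Part A and worsens after a Part B placebo injection stays under ABvac40. The SAESI rule and the post-booster rule also lean towards ABvac40.
- **That an AE present before dosing which worsens afterwards is classed as not treatment-emergent.** The SAP's definition makes it treatment-emergent; the difficulty is identifying it.
- **That the randomised Part A comparison is distorted by cross-product attribution.** Each patient is planned to receive one product in Part A, so this cannot arise there. Part B safety is exploratory.

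**Conclusion.** The point holds in a limited form. For non-SAESIs in the placebo-first sequence, the SAP's rule is out of line with its neighbours and can leave worsening after ABvac40 in the Placebo column of the pooled AE tables. The fields listed in the protocol do not support the worsening criterion used elsewhere in SAP section 7.2.1, including the treatment-emergent definition, and the two emergence definitions overlap.

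The conclusion assumes that no unseen instruction opens a new record at each worsening. Whether the result is a severe Placebo event or a worsening that is not shown depends on what the severity item means, which is not stated. The effect is confined to events without a worsening rule of their own, and the number of patients cannot be derived from the documents. Because a stated rule can misattribute part of the primary safety variable, and the repair is small, it should be corrected before the database containing Part B is locked.

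**What to change.** 1. **SAP section 7.2.1.** Reword the placebo-first non-SAESI rule to: *AEs that start or worsen in severity are associated with the treatment received at the last injection before the start or worsening.* Limit the non-treatment-emergent definition to events that neither start nor worsen at or after the first dose, so that the two definitions exclude each other.
2. **Protocol section 8.3.8 and the eCRF completion instructions.** Enter each increase in severity of an ongoing AE as a new record with its own onset date and severity, linked to the first, or collect a date of severity change. State whether the severity item is the grade at onset or the worst grade. Apply this to both sequences. If the Data Entry Manual already says so, cite it in the SAP.
3. **Data already collected.** Query AEs ongoing at first dose, V1B and V13B for the date of any change in severity, in both sequences.

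The cost is two SAP wording changes, one recording instruction, a short set of queries and a few additional AE records. If the Part A database is already locked, changes to it need the written agreement described in Protocol section 11.3.6.

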8.3.9 Reporting of Serious Adverse Events

Any SAE that occurs after **signing the study ICF through the Final Visit (ie, end of study)** must be expeditiously reported whether or not considered attributable to the study drug. Each SAE must be fully recorded in the subject's eCRF and SAE Report Form. In addition, any SAE that occurs greater than *14 months* after the last dose of the investigational product should be reported if the Investigator feels that the event is related to the use of investigational product.

SAEs will be reported using the designated SAE Report Form. When the Investigator becomes aware of a SAE, she/he must submit a completed, signed and dated SAE Report Form (in English) **within 24 hours** to the [REDACTED] by email/fax. The date of this SAE discovery by the site staff should be documented in the source documents (i.e. medical records).

Each SAE must be followed up until resolution or stabilization. After the initial report, all relevant information for SAE follow-up, and for the outcome, must also be supplied to the Sponsor in a timely manner (within 3 days from its identification or within 24 hours for relevant new information) by means of the SAE Report Form. In addition, the Sponsor or contract research organization (CRO) may request additional information and/or reports.

All SAE Report Forms must be reported to [REDACTED] by email or fax to:

[REDACTED]
[REDACTED]
Fax: [REDACTED]
e-mail: [REDACTED]

When required, and according to local law and regulations, SAEs must be reported to the IRB/EC and regulatory authorities.

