* The First Visit of Part B (V1B) will take place only when the results of the last MRI test performed (either at V21 or V25 or before first vaccination of Part B[‡]) are available and support the vaccination.

‡ A MRI will be performed before first vaccination of Part B only if the previous MRI was performed more than 6 months (±15 days) before V1B.

- ✓ A telephone control interview will take place within the first week (3 ± 3 days) after each vaccination visit.
- ✓ A safety visit will be scheduled two weeks after each vaccination and at V17B.
- ✓ Blood samples will be collected at every safety control visit for safety control and characterization of immune response.
- ✓ Study visits should take place at the Days indicated above, within the following windows:
 - During first 6 months: ± 3 days
 - Between month 6 and month 12: ± 7 days
 - Between month 12 and month 18: ± 15 days
- ✓ If a visit takes place out of window, the patient should be visited as soon as possible; For the five first immunizations the **minimum interval between vaccinations must be 25 days** and the **maximum interval must be 31 days**; if one vaccination is delayed for any reason, the next dose must be re-scheduled to fit this therapeutic window.

In this visit the scanned EKG must be sent to the Medical Advisor for review

§ All patients must be tested for COVID-19 during the Part B vaccination visits before receiving the study medication (see Section 6.1.1.2 for further details)

Phases in the study: visits, assessments and dates:**Part A:**

The Part A of the study will last for up to 104 weeks (from V0 to V25) and at least 18 months (up to V23) during which the patients will receive five monthly (every four weeks) immunizations plus a booster shot. During the study, two interim analyses (Int) will be performed to assess safety, tolerability and biological activity of the treatment (including data from the collected disease biomarkers at each of them). These analyses will be reviewed by an independent Data Safety Monitoring Board (DSMB). The first Int will be carried out once the first 30 patients have completed the 24-week visit (Int-6m) and the second one once all patients have completed the 24-week visit (Int-6m, eight weeks after the fifth monthly immunization) or in October 2020, whichever occurs first.. The double blinding of the study will be maintained throughout these two Int. Additional DSMB reviews may be made *ad hoc* in the event of safety issues.

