22. Participation in another clinical trial within the previous 1 month to screening visit, or within the previous 12 months after the last dose to the screening visit in the case of subjects who participated in trials with a study drug whose intention was to modify the progression AD unless documentation of receipt of placebo is available. The patient cannot be included in the study if the experimental drug was an immunotherapeutic drug, including IVIG or a vaccine against Alzheimer's disease unless documentation of receipt of placebo is available.
23. Patients with alcohol or drug abuse or dependence.
24. Absolute (having a pacemaker or implantable defibrillator) or relative (bare metal stent or stent implanted in the last six months) contraindications to MRI examination. Feeling of claustrophobic do not let perform MRI or PET scan.

25. Patients unlikely to comply with the protocol (e.g., unable to return for follow-up visits).
26. Women of childbearing potential, pregnant or nursing. Note: All women will be considered to be of childbearing potential unless they are postmenopausal (amenorrheic for at least 12 consecutive months, in the appropriate age group, and without other known or suspected cause) or have been sterilized surgically (i.e. bilateral tubal ligation, total hysterectomy, or bilateral oophorectomy, all with surgery at least 1 month before dosing)
27. Significant alterations in the EKG that are associated with an added risk for the patient.

Investigational Product, Dose and Mode of Administration

Study Medication

Name: ABvac40

Active ingredient: Conjugated A β x-40 to KLH

Transporter: Phosphate buffer containing 0.35% aluminium hydroxide (adjuvant)

Pharmaceutical Form: Injection ready vials

Posology: Part A: Verum group: Six administrations: the first five administered once every 4 weeks (28 \pm 3 days) and the sixth at week 42 (V18), 26 weeks after the fifth immunization. Each administration consists of 1mL injection of ABvac40 (containing 0.2 mg of Abetax-40).

Part B: Delayed start group: Six administrations: the first five administered once every 4 weeks (28 \pm 3 days) and the sixth at week 42 (V18B), 26 weeks after the fifth immunization.

Booster group: One administration at week 16 (V13B).

Each administration consists of 1mL injection of ABvac40 (containing 0.2 mg of Abetax-40).

Method of administration: Subcutaneous injection.

Duration of Treatment:

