5.3.4 Follow-up of Subjects Withdrawn from Study Treatment

Subjects who receive any amount of investigational product and discontinue early from the study treatment will be requested to continue with the remaining safety assessment visits (without any more treatment administration nor related phone interviews). The following visits are those considered minimum “safety assessment visits” to be performed in subjects withdrawn from study treatment (as applicable according to the time of withdrawal):

- Safety control visits
 - Face-to-face visits: V3, V6, V9, V12, V15, V16 (Int-6m), V17, V20, V21, V23 and V25 (Final visit) [Part A]; V3B, V6B, V9B, V12B, V15B, V16B, V17B, V20B, V21B and V22B [Part B]

There is no need to perform any additional Vaccination Visit nor phone interviews.

Withdrawn subjects should receive at least a premature discontinuation visit within the 15 days after their last treatment's administration (PDV; see section 4.9.3). If a randomized subject withdraws the study before receiving the first IMP administration, the following assessments of the PDV will not be needed: electrocardiogram; urine analysis (test strip); hemogram, biochemistry, biological activity, MRI, a-PET, CSF.

In accordance with good clinical practice (GCP), patients that discontinue the trial prematurely due to adverse events will be followed-up until resolution of the AE, properly documenting both the cause of premature withdrawal as well as management of data collected and the subsequent treatment received by the patients.

[figure not shown]

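### The 14-month condition for post-study SAE reports fits only the Part A schedule and leaves about 6 months in neither reporting window of Protocol 8.3.9 for the delayed-start group and for patients who end at V23

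*Protocol*

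**What the plan says.** Protocol 8.3.9 sets two windows.

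- **Window 1:** any SAE from "signing the study ICF through the Final Visit (ie, end of study") "must be expeditiously reported whether or not considered attributable to the study drug".
- **Window 2, stated as an addition:** an SAE more than 14 months "after the last dose of the investigational product should be reported if the Investigator feels that the event is related" to the product.

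The dates that decide whether the windows meet are these:

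- **Part A doses** (synopsis, posology): "the sixth at week 42 (V18), 26 weeks after the fifth immunization".
- **Part A length** (synopsis): "The Part A of the study will last for up to 104 weeks (from V0 to V25) and at least 18 months (up to V23").
- **Part B, delayed-start group** (synopsis, posology): "the sixth at week 42 (V18B), 26 weeks after the fifth immunization".
- **Part B, ABvac40 in the Booster group** (synopsis, posology): "Booster group: One administration at week 16 (V13B"). Its remaining Part B injections, including V18B, are placebo.
- **Withdrawn subjects** (Protocol 5.3.4): at least a "premature discontinuation visit within the 15 days after their last treatment".

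Protocol 8.1 names V25 and V22B as the final visits. Protocol 7.2.1.1 also allows V23 as the Part A final visit.

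**The concern.** Window 2 does not begin where window 1 ends. It begins at a fixed distance from the last dose, whatever the date of the subject's last visit. If the last visit comes sooner than 14 months after the last dose, a new SAE in between belongs to neither window. The rule then runs backwards: a related SAE at 15 months is to be reported, while one at 10 months, closer to exposure, is not mentioned.

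The matter is post-study safety capture for an active vaccine. Long-term safety is a stated objective of Part B (Protocol 3.2.1), and the protocol itself accepts that a related SAE may arise beyond 14 months. Two neighbouring sections do not help. Protocol 8.3.8 also ends recording for dosed subjects at the Final Visit, and Protocol 8.4 follows events already present at study completion, not new ones.

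**Working it through.** **Inputs.** Study days and windows come from the Part A and Part B schedules: V18 and V18B day 294 (±7); V13B day 112 (±3); V23 and V22B day 539 (±15); V25 day 728 (±15). The withdrawal visit falls up to 15 days after the last treatment (Protocol 5.3.4). One month = 365.25/12 = 30.44 days, so 14 months = 426 days.

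**Formula.** Gap = 426 days − (day of last visit − day of last dose). Zero or less means that the windows meet.

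**Where the 14 months fits.** V18 to V25: 728 − 294 = 434 days = 62 weeks = 14.3 months. By nominal month this is 24 − 10 = 14. The figure therefore matches the Part A completer.

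**All cases.**

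| Case | Last dose to last visit | Gap |
|---|---|---|
| Part A to V25 | 434 days = 14.3 months | none nominally; up to about 0.5 month at the window extremes |
| Part A ending at V23, no Part B | 539 − 294 = 245 days = 8.0 months | 426 − 245 = 181 days, about 6.0 months |
| Part B delayed start, V18B to V22B | 539 − 294 = 245 days = 35 weeks = 8.0 months | 181 days, about 6.0 months |
| Part B Booster, from the last injection (V18B, placebo) | 245 days = 8.0 months | about 6.0 months |
| Part B Booster, from the last ABvac40 dose (V13B) | 539 − 112 = 427 days = 61 weeks = 14.0 months | none nominally |
| Leaves the study, last visit 15 days after a dose | 15 days = 0.5 month | 426 − 15 = 411 days, about 13.5 months |

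**Range.** With ±7 days at the dose and ±15 at the last visit (22 days in all), the 6.0-month gap runs from 5.2 to 6.7 months. Protocol 4.5 puts the Part B long-term visit 32 weeks after the sixth injection, against 77 − 42 = 35 weeks in the schedule. With 32 weeks (224 days) the gap is 426 − 224 = 202 days, 6.6 months. Those two statements also need reconciling.

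**Which last dose applies in the Booster group.** Protocol 4.7 counts placebo among the investigational product supplies. Protocol 6.1 equates the IMP with ABvac40 and calls placebo the comparator. Sites stay blinded in Part B (Protocol 4.3.3), so an investigator cannot tell which injection was ABvac40 and can only count from the last injection.

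**The case against.** The strongest reply is that the protocol has another route. Protocol 8.3.11.1 sends all expected serious ADRs (ARIA) to expedited reporting. Protocol 8.3.11.2 does the same for all other potentially related SAEs and names aseptic meningo-encephalo-myelitis. Neither sets a time limit. The 24-hour rule in 8.3.9, triggered when the investigator learns of an SAE, is undated too. A reader might infer from the two windows that a vaccine-related SAE in the gap need not be reported at all; the documents do not support that. But both parts of 8.3.11 refer to 8.3.9 for the procedure, and 8.3.9 contains the time windows. So 8.3.11 conflicts with the gap rather than clearly closing it.

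A reader might also infer that every Part B patient has a 6-month gap. That is not established: counted from V13B, the Booster group has none nominally.

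Nor does the expected dropout of about 40% measure how many patients face the 13.5-month gap. Patients who only stop treatment are asked to stay for the remaining safety visits (Protocol 4.9.3 and 5.3.4), and those who stay to V25 have no gap. Patients who leave the study later have shorter gaps. The documents give no split. They also do not say that the withdrawal visit is the Final Visit: 8.3.8 uses withdrawal as an end point only for subjects never dosed, although 8.2.1 records AEs to the last day of participation.

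Finally, the planned safety analysis is not affected, since Protocol 8.1 judges AEs at the final visit. The documents do not state how late these events tend to occur, and no routine MRI follows V22B, so silent ARIA would not surface through this rule. All of that stands, and it limits the point to post-study reporting.

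**Conclusion.** The rule in 8.3.9 is wrong as written. Its 14-month condition fits only V18 to V25. For the delayed-start group, and for Part A patients who end at V23 and do not enter Part B, about 6 months (5.2 to 6.7 with visit windows) fall in neither of its windows. For the Booster group the answer turns on an undefined term: about 6 months from the last injection, none nominally from the last ABvac40 dose. For patients who leave the study altogether soon after a dose the gap could reach about 13.5 months, provided that their last visit counts as the Final Visit; their number is unknown.

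This rests on the literal text of 8.3.9, on nominal visit days, and on V23 counting as the final visit for those who stop there. It makes no claim about how many events would be missed.

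**What to change.** Replace the 14-month sentence in Protocol 8.3.9 with: *any SAE occurring after the subject's last study visit (Final Visit or premature discontinuation visit) must be reported if the Investigator considers it related*. The second window then starts where the first ends, so every gap in the table becomes zero, and this rule no longer depends on what counts as the last dose. Reconcile 8.3.11.1 and 8.3.11.2 with the new sentence, so that the duty to report serious ADRs and the procedure they refer to cover the same period.

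The cost is one amended sentence with its cross-references and a few extra post-study reports. No visits are added.
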